8.4.1.2. Comparative Tolerability

8.4.1.2.1. Research Objective and Question

The research objective for comparative tolerability is specified according to the taxonomy of PRO research objectives by the Setting International Standards in Analyzing Patient-Reported Outcomes and Quality of Life Endpoints Data (SISAQOL) Consortium (Coens et al. 2019) as follows:

- to demonstrate superior tolerability of Arm A as compared to Arm B in patients with progressive, advanced, kinase inhibitor naïve, RET-mutant MTC.

The associated research question is:

- what is the difference in the mean proportion of time on treatment with high side effect both among patients treated in Arm A compared to those treated in Arm B?

8.4.1.2.2. Definition of Endpoint

The estimand for this secondary objective is described by the following attributes:

- Population: patients with progressive, advanced, kinase inhibitor-naïve, RET-mutant MTC. Further details can be found in Section [8.4.1.2.3](#).
- Endpoint:
 - A single item “I am bothered by side effects of treatment” from the Functional Assessment of Cancer Therapy (FACT) general scale will be utilized to assess overall treatment side-effect burden. The Functional Assessment of Cancer Therapy-Side Effects (FACT-GP5) item is measured on a 5-item Likert scale: 0 (not at all); 1 (a little bit); 2 (somewhat); 3 (quite a bit); or 4 (very much). This item will be completed weekly by the patient via an electronic clinical outcomes assessment (eCOA) device provided; sites will not administer this instrument.
 - Comparative tolerability is defined as a comparison of the proportion of time on treatment with a high symptom burden as assessed by the FACT-GP5 between Arm A and Arm B. High symptom burden is defined as a FACT-GP5 score of 3 or 4 (ie “Quite a bit” or “Very much” on a 5-point Likert scale). This proportion will be calculated for each patient using:
 - As numerator - the cumulative amount of time, in weeks, during which a patient reports high side effect burden (ie selects a score of 3 or 4 on the FACT-GP5 response scale).
 - As denominator - the total duration of therapy (weeks), derived as (date of last study treatment dose - date of first study treatment dose + 1) ÷ 7.
- Treatment condition: the randomized study intervention (selpercatinib or cabozantinib/vandetanib) will be administered twice or once a day in continuous 28-day cycles until disease progression, unacceptable toxicity or other protocol-defined reasons for treatment discontinuation. Further details on study interventions including interventions, concomitant therapy and dose modification can be found in Protocol Section 6 Study Intervention.
- Intercurrent-event strategies for main analytical approach are listed in [Table JZJB.9](#).

- Population-level summary measure: difference in the proportion of time with high side effect bother in selpercatinib versus cabozantinib/vandetanib

Table JZJB.9. Intercurrent Events of Comparative Tolerability

Intercurrent Event	IES
Treatment discontinuation for any reason (including disease progression or death)	“While on treatment” strategy: the proportion of time with high side effect bother is calculated using treatment exposure in the denominator of the endpoint, so any treatment discontinuation is taken into account by design
Nonadherence to the study treatment	“Treatment policy” strategy: no modification will be made to the calculation of the proportion of time with high side effect bother to take into account the adherence of the patient to the treatment

Abbreviation: IES = Intercurrent-Event Strategies.

8.4.1.2.3. Main Analytical Approach

Comparative tolerability is also a key secondary endpoint and will be tested conditionally on achieving a statistical significance for PFS and TFFS by BICR to preserve the overall Type I error rate at the 1-sided significance level of 0.025 (see Section 8.8 Interim Analyses for details).

The proportion of time with high side effect bother will be compared between treatment arms using the van Elteren test (van Elteren 1960), a stratified Wilcoxon rank sum test (Wilcoxon 1946), stratified by the 2 randomization strata based on IWRS data: RET mutation (M918T vs. other) and intended control treatment (cabozantinib vs. vandetanib).

Comparative tolerability will be analyzed in the Tolerability Evaluable Population as defined in Section 7, ie patients enrolled by the time of the interim analysis (approximately 250 patients projected to be enrolled) regardless of the sample size re-estimation result. Since the sample size is fixed for the comparative tolerability endpoint, no adjustment of test statistic will be applied and the Type I error will not be inflated by a potential sample size increase.

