8.4.1.2.6. Supplementary Analyses

8.4.1.2.6.1. Comparison of Selpercatinib Versus Cabozantinib and Vandetanib Separately

A subgroup analysis will be conducted based on a stratification factor of intended treatment if subsequently randomized to control arm to estimate the difference in proportion of time with high side effect bother between selpercatinib and each of the 2 treatment options of the control arm. The same analytical approach will be used as for the main analysis.

8.4.1.2.6.2. Other Analytical Approaches

No prior FACT-GP5 data of MTC patients is available to inform the distribution of proportion of time with high side effect bother. Without a valid assumption of the distribution, nonparametric approaches are used in the main analysis. Depending on the empirical distribution observed at the time of analysis, multivariable linear regressions with original value and with proper transformations of proportion of time with high side effect bother (eg logit transformation) will be performed as supplementary analyses. The difference in mean proportion of time with high

side effect bother between treatment arms with 95% CI will be estimated using the multivariable linear regressions. Proportion of time with high side effect bother (with or without transformation) will be used as the outcome variable, treatment group (Arm A vs. Arm B) as the explanatory variable, and the 2 randomization strata as covariates. Other advanced analytical approaches may also be performed as deemed appropriate.

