The figure below provides an overview of the proposed adaptive design. Sample size/total number of events determination will be conducted at the interim efficacy analysis. If the study is not declared positive, final analysis will be conducted according to a determination zone (favorable, promising, or unfavorable) where the interim results fall. At final analysis, the study will be declared positive if the critical boundary is met.

Abbreviations: IF=Information Fraction; HR=Hazard Ratio

Figure JZJB.1 Overview of Proposed Adaptive Design

Conditional on PFS by BICR achieving statistical significance, TFFS by BICR will be tested and then comparative tolerability. Both TFFS and comparative tolerability will be formally tested at most once at final analysis. A nominal alpha of 0.00001 will be spent for interim analysis and both key secondary endpoints will be tested against 1-sided significance level of 0.02499 at final analysis.

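### The alpha-controlled tolerability test is a rank test, but the SAP's research question and summary measure are not rank-based and no matching effect estimate is planned

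*SAP*

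**What the plan says.** Four parts of the SAP describe this endpoint, and they do not name one quantity.

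- **Research question (8.4.1.2.1).** It asks "what is the difference in the mean proportion of time on treatment with high side effect" bother, Arm A against Arm B. The objective above it is "to demonstrate superior tolerability of Arm A as compared to Arm B".
- **Estimand attribute (8.4.1.2.2).** "Population-level summary measure: difference in the proportion of time with high side effect bother in selpercatinib versus cabozantinib/vandetanib". It does not say whether this is a difference in means, in medians or something else.
- **Confirmatory test (8.4.1.2.3).** "The proportion of time with high side effect bother will be compared between treatment arms using the van Elteren test", stratified by the two randomization factors.
- **Supplementary analyses (8.4.1.2.6).** These give the reason for a rank test, namely that no earlier FACT-GP5 data in this disease exist: "Without a valid assumption of the distribution, nonparametric approaches are used in the main analysis". They also plan linear regressions, on the original scale and on transformed scales depending on the distribution observed, which yield a mean difference with a 95% CI.

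The test comes last in the hierarchy, after PFS and TFFS. SAP 8.8 says that "both key secondary endpoints will be tested against 1-sided significance level of 0.02499 at final analysis". Protocol 9.4.3.2.2 describes the endpoint only as a comparison of the proportion of time and leaves the method to the SAP. Neither document plans a rank-based effect estimate, such as a Mann-Whitney probability or a Hodges-Lehmann shift.

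**The concern.** A rank-sum test responds to which arm's patients tend to have the smaller values. It does not respond to how far apart the means are. For an outcome bounded by 0 and 1, where many patients may sit at exactly 0, the two can disagree. If fewer selpercatinib patients are affected, but each for a larger share of treatment time, the ranks favour selpercatinib while the means are equal or reversed. If more are affected, but each only briefly, a genuinely lower mean can go undetected.

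What is at stake is how the last type I error-controlled result may be read. As written, a significant p-value answers a question that the SAP does not pose, and no estimate on the same scale as that p-value accompanies it. The primary endpoint is not affected.

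**Working it through.** **1. The plan's own figure.** "A nominal alpha of 0.00001 will be spent for interim analysis", and 0.02499 is left for the final analysis. 0.00001 + 0.02499 = 0.02500, so the stated level reproduces. No effect size, SD or power is given for this endpoint.

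**2. What van Elteren measures.** In stratum *h*, let θ_h be the share of Arm A/Arm B patient pairs in which the Arm A patient has less high-bother time, ties counted half. The Arm A rank sum minus its null expectation equals n_A·n_B·(½ − θ_h). With stratum weights 1/(N+1), the numerator of the statistic is Σ [n_A·n_B/(N+1)]·(½ − θ_h). No mean enters.

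**3. One case by hand (assumed shapes).**
- Arm A: 75% of patients at 0, the rest Beta(2,2) with mean 0.50. Overall mean 0.25 × 0.50 = 0.125.
- Arm B: 50% at 0, the rest Beta(1,3) with mean 0.25. Overall mean 0.50 × 0.25 = 0.125.
- Pairs with A at 0 and B above 0: 0.75 × 0.50 = 0.375. Both at 0: 0.375, of which half counts, 0.1875. Both above 0: 0.25 × 0.50 = 0.125.
- Among pairs with both above 0, the chance that A is smaller is E[(1−X)³] for X ~ Beta(2,2) = (2·3·4)/(4·5·6) = 0.20.
- θ = 0.375 + 0.1875 + 0.125 × 0.20 = 0.5875.

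The mean difference is 0, yet θ exceeds ½. If affected Arm A patients follow Beta(3,2) instead (mean 0.60, overall 0.25 × 0.60 = 0.150), the chance is (2·3·4)/(5·6·7) = 0.114. Then θ = 0.5625 + 0.125 × 0.114 = 0.577: still above ½, with Arm A worse on the mean.

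**4. Simulation at the planned size.** From the documents: about 250 patients, 2:1 (167 and 83), four strata, 1-sided 0.02499. Assumed: stratum shares 0.36/0.24/0.24/0.16, and each patient's proportion drawn as a point mass at 0 plus a Beta distribution. There were 4000 trials per row, with a tie-corrected van Elteren statistic. The comparator was a strata-adjusted linear regression with robust standard error.

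| Scenario | Affected, A vs B | Mean among affected | Overall mean | van Elteren favours A | Mean test favours A |
|---|---|---|---|---|---|
| Identical arms | 50% vs 50% | 0.25 vs 0.25 | 0.125 vs 0.125 | 2.1% | 1.6% |
| Equal means, mild shape difference | 40% vs 50% | 0.3125 vs 0.25 | 0.125 vs 0.125 | 17.1% | 2.6% |
| Equal means, large | 25% vs 50% | 0.50 vs 0.25 | 0.125 vs 0.125 | 75.6% | 2.2% |
| Equal means, large | 30% vs 60% | 0.40 vs 0.20 | 0.120 vs 0.120 | 81.5% | 2.1% |
| A worse | 25% vs 50% | 0.60 vs 0.25 | 0.150 vs 0.125 | 64.2% | 0.4% |
| A worse | 30% vs 60% | 0.50 vs 0.20 | 0.150 vs 0.120 | 67.7% | 0.1% |
| A better, same severity | 30% vs 55% | 0.25 vs 0.25 | 0.075 vs 0.138 | 94.8% | 74.7% |
| A better on the mean, more affected | 60% vs 40% | 0.15 vs 0.40 | 0.090 vs 0.160 | 2.1% | 76.8% |

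In the last row van Elteren favours Arm B in 7.6%. A smaller crossing, 45% vs 50% affected with equal means, gives about 6% in favour of A.

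**The case against.** Much can be said for the plan, and most of it stands.

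- **The test is valid for its own hypothesis.** With identical distributions it rejects at 2.1%, and it agrees with the means when one arm is better throughout. A reader might infer from the large percentages that type I error is broken. It is not: those are rejections under equal means with unequal shapes, which is a different null hypothesis.
- **The formal summary measure does not say mean.** A reader might infer that the estimand is a mean difference. The word is in the research question and the supplementary regressions only, and Protocol 9.4.3.2.2 does not use it. The documented fault is an unspecified summary measure and a question that does not fit the test.
- **The mean is not hidden.** The supplementary regressions give it with a 95% CI, so a zero or reversed difference could be seen. It lies outside alpha control, and nothing ties the reading of the rank test to it.
- **The documents do not say that a significant result will be reported as a lower mean.** That is an inference. The stated objective is superior tolerability.
- **The large rates need large crossings.** Nothing in the documents supports such shapes. Nothing rules them out either, since the SAP says it has no prior data.
- **A mean test has a price.** When selpercatinib simply affects fewer patients at the same severity, power falls from 94.8% to 74.7% in the table. In runs with a permutation test of means it falls from 90% to 73% (25% vs 46% affected) and from 84% to 61% (30% vs 50%). An unstudentized permutation test is also not exact for equal means with unequal shapes: with A 60% affected at 0.25 and B 30% at 0.50, it favours A in 3.9%, against 1.9% for a Welch-type test.

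One defence does not stand. Having no distributional model is a reason to avoid a parametric analysis. It does not settle which quantity is the target, and the SAP should still name it.

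**Conclusion.** The mismatch is in the SAP's text: the question concerns a mean, the summary measure is unspecified, the alpha-controlled test is rank-based, and no estimate belongs to that test. It can act in either direction. A significant result could stand beside a zero or reversed mean difference, or a real mean benefit could be missed.

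Its size depends on shapes that the documents do not give. With equal means, the assumed scenarios run from about 6% through 17.1% to 81.5% in favour of selpercatinib. These figures show what is possible and are not a forecast.

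The documents do not support the conclusion that van Elteren is the wrong confirmatory test or must be replaced. What needs correcting is the stated target, the missing estimate and the limits on interpretation.

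**What to change.** Keep van Elteren as the confirmatory test and amend the SAP as follows.

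1. In 8.4.1.2.1 and 8.4.1.2.2, restate the question and the summary measure as the stratified probability that an Arm A patient has less high-bother time than an Arm B patient, ties counted half.
2. In 8.4.1.2.3, report that estimate with a 95% CI. Stratum weights n_A·n_B/(N+1) would match the test statistic.
3. Beside it, report the strata-adjusted mean difference on the untransformed scale with a robust or bootstrap 95% CI, whatever distribution is observed.
4. State that van Elteren significance alone does not support a claim of a lower mean proportion of time.

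The cost is SAP wording and a short program. No new data are needed, and neither the power of the confirmatory test nor the alpha hierarchy changes.

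Making a mean-difference test confirmatory is an option if the mean is what the sponsor wants to claim. It would need a studentized statistic, and it costs roughly 20 points of power when the arms differ mainly in how many patients are affected (94.8 − 74.7 = 20.1; 90 − 73 = 17; 84 − 61 = 23).

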8.4.1.2.4. Missing Data Handling

Missing data can occur at 2 levels in this analysis:

- at the individual FACT-GP5 assessment time points, and
- at the patient level if there are too many consecutive, missing FACT-GP5 assessments for a given patient (making the calculation of the proportion of time with high side effect bother for this patient too uncertain).

Missing individual FACT-GP5 assessments will be handled in the calculation of the proportion of time with high side effect. The following rules will be applied to calculate the proportion in case of missing FACT-GP5 assessments:

1. If 1 or 2 consecutive FACT-GP5 assessments are missing, they will be imputed according to the available FACT-GP5 assessments as follows:
 - If both the FACT-GP5 assessments immediately before and immediately after the missing assessment(s) indicate no high side effect bother, then the missing assessment(s) will be considered as indicating no high side effect bother.

- If any 1 of the FACT-GP5 assessments immediately before or immediately after the missing assessment(s) indicate high side effect bother, then the missing assessments will be considered as indicating high side effect bother.
 - A missing FACT-GP5 at baseline will not be imputed nor will it inform the imputation of other missing values, as it relates to the period before treatment start and is not included in the calculation of proportion of time with high side effect bother.
 - For patients for whom Cycle 1 Day 8 is missing, only Cycle 1 Day 15 will be used to impute the missing value. If both Cycle 1 Day 8 and Cycle 1 Day 15 are missing, only Day 15 can be imputed from Day 21. Day 8 will not be imputed and will be considered missing.
2. If 3 or more consecutive FACT-GP5 assessments are missing, the period corresponding to these missing assessments will be subtracted from both the numerator and denominator
 3. If FACT-GP5 assessments are missing before treatment discontinuation, they will be imputed as follows:
 - If 1 or 2 FACT-GP5 assessments are missing immediately before discontinuation, they will be given the same value as indicated by the last available FACT-GP5 assessment.
 - If 3 or more FACT-GP5 assessments are missing immediately before discontinuation, then the period corresponding to these missing assessments will be subtracted from both the numerator and denominator.

The distribution of missing data will be summarized by treatment arm. The impact of missing data on the results at patient level will be explored in the sensitivity analyses.

8.4.1.2.5. Sensitivity Analyses

8.4.1.2.5.1. Impact of Threshold Used to Define High Side Effect Bother

In the main analysis of the comparative tolerability endpoint, the proportion of time with high side effect bother is calculated under the assumption that a FACT-GP5 score of ≥ 3 characterizes high side effect bother for the patient. Sensitivity analyses will be conducted to explore the impact of this assumption on the conclusion of the comparison between the treatment arms by considering different thresholds for the FACT-GP5 score for the calculation. The analyses will be replicated with the following calculations of proportion of time: proportion of time with a FACT-GP5 score ≥ 2 and proportion of time with a FACT-GP5 score of 4.

8.4.1.2.5.2. Impact of Imputation Rule for Missing FACT-GP5 Assessment in Calculation of Proportion of Time with High Side Effect Bother

The calculation of proportion of time with high side effect bother, as specified above for the main analyses, includes a rule for imputing missing FACT-GP5 assessments. The impact of this imputation rule will be explored by replicating the analysis using alternative approaches for the management of missing FACT-GP5 assessments in the calculation of the proportion of time with high side effect bother. The following imputation strategy will be applied:

- **Most conservative imputation strategy** - any missing FACT-GP5 assessment is considered indicative of high side effect bother.
- **Least conservative imputation strategy** - any missing FACT-GP5 assessment is considered indicative of no high side effect bother.
- **No imputation** - No imputation is made for any missing FACT-GP5 assessments; all periods of missing data are excluded from both the numerator and denominator.

8.4.1.2.5.3. Impact of Patients with Prolonged Periods of Consecutive Missing FACT-GP5 Assessments

In the main analysis of the comparative tolerability endpoint, all patients of the Tolerability Evaluable Population will be included. However, for some patients, due to prolonged periods of consecutive missing FACT-GP5 assessments, side effect bother cannot be imputed per the rules defined in Section 8.4.1.2.3 for every missing FACT-GP5 assessments over the course of treatment. If patients have very high missingness, inclusion of the patients may impact the interpretation of outcomes. To evaluate the impact of patients with prolonged periods of consecutive missing FACT-GP5 assessments, sensitivity analyses will be performed by replicating the main analysis in the following subpopulations of the Tolerability Evaluable Population patients:

- for whom side effect bother, as assessed by the FACT-GP5 item, is available or can be imputed for $\geq 50\%$ of the total duration of treatment.
- for whom side effect bother, as assessed by the FACT-GP5 item, is available or can be imputed for $\geq 80\%$ of the total duration of treatment.
- for whom side effect bother, as assessed by the FACT-GP5 item, is available or can be imputed for $\geq 90\%$ of the total duration of treatment.
- for whom side effect bother, as assessed by the FACT-GP5 item, is available or can be imputed for 100% of the total duration of treatment.

8.4.1.2.6. Supplementary Analyses

8.4.1.2.6.1. Comparison of Selpercatinib Versus Cabozantinib and Vandetanib Separately

A subgroup analysis will be conducted based on a stratification factor of intended treatment if subsequently randomized to control arm to estimate the difference in proportion of time with high side effect bother between selpercatinib and each of the 2 treatment options of the control arm. The same analytical approach will be used as for the main analysis.

8.4.1.2.6.2. Other Analytical Approaches

No prior FACT-GP5 data of MTC patients is available to inform the distribution of proportion of time with high side effect bother. Without a valid assumption of the distribution, nonparametric approaches are used in the main analysis. Depending on the empirical distribution observed at the time of analysis, multivariable linear regressions with original value and with proper transformations of proportion of time with high side effect bother (eg logit transformation) will be performed as supplementary analyses. The difference in mean proportion of time with high

side effect bother between treatment arms with 95% CI will be estimated using the multivariable linear regressions. Proportion of time with high side effect bother (with or without transformation) will be used as the outcome variable, treatment group (Arm A vs. Arm B) as the explanatory variable, and the 2 randomization strata as covariates. Other advanced analytical approaches may also be performed as deemed appropriate.

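### Comparative tolerability: the logit-transformed regression is undefined at 0% or 100% high-bother time and does not estimate the stated mean difference; one proportion-scale estimate should be named in advance

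*SAP*

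**What the plan says.** SAP 8.4.1.2.2 gives each patient a proportion. The numerator is the number of weeks with a FACT-GP5 score of 3 or 4, and the denominator is the duration of therapy in weeks. The intercurrent-event table in that section confirms that "the proportion of time with high side effect bother is calculated using treatment exposure in the denominator of the endpoint". The population-level summary measure, also there, is the between-arm difference in this proportion. The research question in 8.4.1.2.1 asks about the difference in its mean.

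The main test is a rank test (8.4.1.2.3): "The proportion of time with high side effect bother will be compared between treatment arms using the van Elteren test", stratified by the two randomization factors. Under SAP 8.8 it is tested at one-sided 0.02499 at the final analysis, after PFS and TFFS.

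The effect size with its interval is planned in 8.4.1.2.6.2. That section first concedes that "No prior FACT-GP5 data of MTC patients is available to inform the distribution of proportion of time with high side effect bother". The models it plans are "multivariable linear regressions with original value and with proper transformations of proportion of time with high side effect bother (eg logit transformation", the logit being the only transformation named. Their choice is left open ("Depending on the empirical distribution observed at the time of analysis"), and they rank below the main test: they "will be performed as supplementary analyses". The same models supply the mean difference and its interval; the sentence ends "side effect bother between treatment arms with 95% CI will be estimated using the multivariable linear regressions". On the outcome: "Proportion of time with high side effect bother (with or without transformation) will be used as the outcome variable". The SAP gives no rule for choosing a transformation, for handling values of 0 or 1 under a logit, or for returning a transformed coefficient to the proportion scale. It does not say which standard errors are used.

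**The concern.** A patient who never scores 3 or 4 has a value of exactly 0, and one who scores 3 or 4 in every counted week has a value of 1. Nothing in the SAP prevents either. The Tolerability Evaluable set (SAP 7) requires a first dose at least 6 months before cutoff, not 6 months of treatment, so patients with few weekly readings stay in. The imputation rules (8.4.1.2.4) fill gaps of one or two assessments between non-high scores as non-high, which preserves zeros.

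The logit is undefined at both values. An analyst who chose it would have to drop those patients or invent a constant, and dropping zeros removes the patients with the best tolerability, possibly unequally by arm. Even with no boundary values, the coefficient is a difference in mean log-odds and not a difference in mean proportion.

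The rank test gives a p-value but no mean difference. If it succeeds, readers will want the size of the gain with an interval. The SAP leaves it until the data are seen which regression supplies that.

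**Working it through.** The documents state no power, standard deviation, effect size or boundary share for this endpoint, so there is no planned figure to reproduce. All distributional inputs below are assumptions. The figure of about 250 patients (8.4.1.2.3) and the 2:1 allocation (SAP 4.2) come from the SAP and give 167 and 83.

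**1. The logit at the boundary.** logit(p) = ln(p/(1-p)). At p = 0 it is minus infinity and at p = 1 plus infinity.

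**2. Why the constant matters.** Replace 0 by c and 1 by 1-c. If c is below every interior value, moving from c1 to c2 shifts the treatment coefficient by [(zA - zB) - (oA - oB)] × [logit(c2) - logit(c1)], where z and o are the shares at 0 and 1. With logit(0.0001) = -9.210 and logit(0.001) = -6.907, the second factor is 2.303.

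- Zeros 10% / 5%, ones 1% / 1%: 0.05 × 2.303 = 0.115
- Zeros 40% / 20%, ones 1% / 3%: 0.22 × 2.303 = 0.507
- Zeros 70% / 40%, ones 1% / 3%: 0.32 × 2.303 = 0.737
- Zeros 60% / 35%, ones 1% / 1%: 0.25 × 2.303 = 0.576

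The corresponding shifts in simulation were 0.116, 0.505, 0.736 and 0.573.

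**3. Simulation.** There were 1,000 trials per scenario, with 26 to 104 weekly readings per patient, no strata covariates, and interior proportions from beta distributions. Their means (A / B) were 15% / 25%, 15% / 25%, 20% / 25% and 25% / 25%. Constants were 0.025, 0.01, 0.001 and 0.0001.

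| Zeros A / B | Logit coefficient, constant 0.025 to 0.0001 | Boundary patients dropped (share kept) | Original-value difference |
|---|---|---|---|
| 10% / 5% | -0.78 to -1.13 | -0.84 (91%) | -0.10 |
| 40% / 20% | -0.98 to -2.23 | -0.84 (65%) | -0.12 |
| 70% / 40% | -0.86 to -2.62 | -0.40 (38%) | -0.11 |
| 60% / 35%, same interior mean | -0.53 to -1.89 | +0.02 (47%) | -0.06 |

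The largest coefficient is 1.4, 2.3, 3.1 and 3.6 times the smallest in the four rows. In the last row the arms differ only in zeros, so dropping boundary patients removes the effect. The original-value regression keeps everyone and needs no constant.

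**4. A second set of assumptions, enumerated exactly.** Patient rates are Beta(0.3, 2.7) over 80 weeks in Arm A (mean 0.3/3 = 10%) and Beta(0.6, 2.4) over 45 weeks in Arm B (mean 0.6/3 = 20%). P(0) = B(a, b+w)/B(a, b), where B is the beta function and w the weeks, gives 34.5% and 15.9%; exact ones are negligible. Overall (2 × 34.5 + 15.9)/3 = 28.3% are at the boundary. The logit coefficient is -1.91, -1.49, -1.06 and -0.83 for constants 0.0001, 0.001, 0.01 and 0.025, and -0.76 if boundary patients are dropped. The difference in mean proportion is 10% - 20% = -0.100. A fractional logistic model with treatment alone is saturated, so its standardized difference is also -0.100, with no constant.

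**5. Standard errors for the untransformed model.** Let the control-arm variance be r times that of Arm A, with 2n and n patients. The true variance of the mean difference is proportional to 1/2 + r. Constant-variance least squares estimates [(2 + r)/3] × (3/2) = 1 + r/2. Coverage of a nominal 95% interval is 2Φ(1.96 × √[(1 + r/2)/(1/2 + r)]) - 1.

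- r = 1: 95%
- r = 2: ratio 0.80, coverage 92.0%
- r = 3: ratio 0.714, coverage 90.2%

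Under step 4 the variances are 0.09/4 + 0.0675/80 = 0.0233 and 0.16/4 + 0.12/45 = 0.0427, so r = 1.83 and coverage is about 92.4%. Robust standard errors restore about 95%.

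**The case against.** The strongest reply is that the remedy is already in the same sentence. The original-value regression includes every patient, needs no constant, and gives the stated difference with an interval. The logit is only an example, restricted to proper transformations and conditional on the observed distribution; an analyst facing a spike at zero might not use it. The analyses are supplementary, and the error-controlled van Elteren test is well defined at 0 and 1. SAP 8.1 also plans means for continuous variables, so the raw difference would be visible in any case. All of this stands.

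Three stronger readings are therefore not supported:

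- A reader might infer that the reported tolerability effect as a whole hangs on dropped patients or a constant. That is true only of a logit version.
- A reader might infer that many patients will sit at 0 or 1. The SAP says no prior data inform the distribution, and with few zeros the spread is modest.
- A reader might infer a threat to the key secondary test. Choosing a supplementary transformation late does not touch its type I error.

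It is also fair that 0.0001 is far finer than the data: one week in 80 is 0.0125. Between constants of 0.01 and 0.025 the simulated coefficients move less, from -0.90 to -0.78 in the first scenario and from -1.15 to -0.86 in the third. The sensitivity to dropping remains.

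What the reply leaves open is that the SAP does not say which regression supplies the reported estimate, and that the one transformation it names neither handles the endpoint's boundary values nor targets the stated difference.

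**Conclusion.** The point holds as a minor gap in a supplementary analysis. It rests on two facts: the endpoint definition permits exact 0 and 1, and the SAP attributes the mean difference to regressions with or without transformation without separating the scales. No distributional assumption is needed for that. The size is unknown because the boundary share is unknown. Under the assumed scenarios the logit coefficient varies 1.4-fold to 3.6-fold across constants, and dropping boundary patients ranges from nearly harmless to removing the effect. The case for robust standard errors is conditional too: the shortfall to about 90% to 92% coverage arises when control-arm values are two to three times as variable, and the SAP is silent on the standard errors.

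**What to change.** In SAP 8.4.1.2.6.2, name before the data are seen one reported estimate on the proportion scale, with its 95% CI, to stand beside the van Elteren p-value. Either of these serves:

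- the untransformed difference adjusted for the two randomization strata, with heteroscedasticity-consistent standard errors; or
- the standardized difference in mean proportion from a fractional logistic model (binomial quasi-likelihood, logit link, robust variance) with treatment and the two strata.

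Replace the logit-transformed linear regression with the fractional logistic model, which accepts exact 0 and 1. Whichever estimate is not named can remain as a check.

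The cost is a small wording change, using standard software and no new data. The interval may be slightly wider than the default least-squares one.
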